#### **2.1.4.4 Vital signs variables**

Vital signs include: heart rate (HR), systolic blood pressure (BP) and diastolic BP, and body temperature in sitting position.

## **2.2 DISPOSITION OF PATIENTS**

This section describes patient disposition for both patient study status and the patient analysis populations.

Screened patients are defined as any patients who met the inclusion criteria and signed the informed consent.

Randomized patients consist of all patients with a signed informed consent form who have had a treatment kit number allocated and recorded in the IRT database, regardless of whether the treatment kit was used.

For any patient randomized more than once, only the data associated with the first randomization will be used in any analysis population. The safety experience associated with any later randomization will be assessed separately.

The safety experience of patients treated and not randomized will be reported separately, and these patients will not be in the safety population.

For patient study status, the total number of patients in each of the following categories will be presented in the clinical study report using a flowchart diagram or summary table:

- Screened patients;
- Screen failure patients and reasons for screen failure;
- Nonrandomized but treated patients, if any;
- Randomized patients;
- Randomized but not treated patients;
- Randomized and treated patients;
- Patients who did not complete the study treatment period as per protocol;
- Patients who discontinued study treatment by main reason for permanent treatment discontinuation (For the case of treatment discontinuation due to adverse event which is provided in CRF by investigators, medical expert will conduct a blinded review on the adverse event or pre-specify a rule to distinguish the “adverse event” or “CKD worsening underwent dialysis” before database lock);
- Status at last study contact.

For all categories of patients (except for the screened and nonrandomized categories) percentages will be calculated using the number of randomized patients as the denominator divided by the number of exposed patients.

Reasons for treatment discontinuation will be supplied in tables giving numbers and percentages by treatment group.

All critical or major deviations potentially impacting efficacy analyses, randomization, and drug-dispensing irregularities, and other major or critical deviations will be summarized in tables giving numbers and percentages of deviations by treatment group.

Additionally, the analysis populations for safety, efficacy will be summarized in a table by number of patients on the randomized population:

- Randomized population
- Efficacy population: modified intent-to-treat (mITT) population
- Safety population

Definitions of the study population are provided in [Section 2.3](#).

## 2.2.1 Randomization and drug dispensing irregularities

Randomization and drug-dispensing irregularities occur whenever:

1. A randomization is not in accordance with the protocol-defined randomization method, such as a) an ineligible patient is randomized, b) a patient is randomized based on an incorrect stratum, c) a patient is randomized twice, or d) in a dynamic randomization scheme the treatment assignment is, in fact, not random, due to a computer program error.

OR

2. A patient is dispensed an IMP kit not allocated by the protocol-defined randomization, such as a) a patient at any time in the study is dispensed a different treatment kit than as randomized (which may or may not contain the correct-as-randomized IMP), or b) a nonrandomized patient is treated with IMP reserved for randomized patients.

Randomization and drug-dispensing irregularities will be monitored throughout the study and reviewed on an ongoing basis.

All randomization and drug-dispensing irregularities will be documented in the clinical study report. If the number of irregularities is large enough to make a tabular summary useful, the irregularities will be categorized and summarized among randomized patients (number and percentages). Nonrandomized, treated patients will be described separately.

Randomization and drug-dispensing irregularities to be prospectively identified include but are not limited to:

---

### ***Randomization and drug allocation irregularities***

---

*Kit dispensation without IRT transaction*

*Erroneous kit dispensation*

*Kit not available*

*Randomization by error*

*Patient randomized twice*

*Stratification error*

---

## 2.3 ANALYSIS POPULATIONS

Patients treated without being randomized will not be considered randomized and will not be included in any efficacy population.

Patients who are dispensed study drug without calling the IRT or before calling the IRT are considered nonrandomized patients. They are excluded from any population for analysis, including safety. However, if these patients experienced any significant safety event, they should be documented separately in the clinical study report.

### 2.3.1 Efficacy populations

The primary efficacy analysis population will be the mITT population.

#### 2.3.1.1 *Modified intent-to-treat population*

Modified Intent-to-treat (mITT) population: The mITT population consists of all patients who are randomized, receive at least one dose of IMP, and have both a baseline assessment and at least one post-baseline assessment of phosphorus measure.

### 2.3.2 Safety population

Safety population: The safety population consists of all randomized patients who receive at least one dose of IMP.

In addition:

- Nonrandomized but treated patients with IMP will not be part of the safety population, but their safety data will be presented separately.
- Randomized patients for whom it is unclear whether they took the study medication will be included in the safety population as randomized.
- For patients receiving more than 1 study treatment during the trial, the treatment group allocation for as-treated analysis will be in Renvela group.

## 2.4 STATISTICAL METHODS

### 2.4.1 Demographics and baseline characteristics

Continuous data will be summarized using the number of available data, mean, standard deviation (SD), median, minimum, and maximum for each treatment group. First quartile (Q1) and third quartile (Q3) will be provided for baseline serum phosphorus. Categorical and ordinal data will be summarized using the number and percentage of patients in each treatment group.

Parameters will be summarized on the randomized population and analyzed by the treatment group to which they were randomized. In the randomized population, parameters will also be summarized within each randomization stratum as per IVRS.

Parameters described in [Section 2.1.1](#) will be summarized by treatment group and overall treatment groups using descriptive statistics.

All reported patient's medical and surgical history will be presented by primary SOC and PT.

The tables will be sorted by SOC internationally agreed order and decreasing frequency of PT based on the overall incidence across treatment groups. In addition all medical history of specific interest (see [Section 2.1.1](#)) will be presented by treatment group.

## 2.4.2 Prior or concomitant medications

The prior and concomitant medications will be presented for the safety population.

Medications will be summarized by treatment group according to the WHO-DD dictionary, considering the first digit of the anatomic category (ATC) class (anatomic category) and the first 3 digits of the ATC class (therapeutic category). A given medication may be classified in more than 1 ATC class. All ATC codes corresponding to a medication will be summarized, and patients will be counted once in each ATC category (anatomic or therapeutic) linked to the medication. Therefore patients may be counted several times for the same medication.

The table for prior medications and concomitant medications will be presented by anatomic category, therapeutic category and generic medication name, sorted by decreasing frequency of ATC and generic medication name based on the overall incidence in Renvela group. In case of equal frequency regarding ATCs (anatomic, therapeutic categories or generic medication name), alphabetical order will be used.

The use of concomitant Native Vitamin D will be summarized by treatment group.

## 2.4.3 Extent of investigational medicinal product exposure and compliance

The extent of IMP exposure and compliance will be assessed and summarized by actual treatment within the safety population ([Section 2.3.2](#)).

### 2.4.3.1 *Extent of investigational medicinal product exposure*

The extent of IMP exposure will be assessed by the duration of IMP exposure, and actual dose information.

Duration of IMP exposure is defined as last dose date – first dose date + 1 day, regardless of unplanned intermittent discontinuations (see [Section 2.5.2](#) for calculation in case of missing or incomplete data). Non-integer values will be rounded to 1 decimal place.

Duration of IMP exposure will be summarized using number, mean, SD, median, minimum, and maximum. In addition, the durations of treatment exposure will be summarized the percentage of patients according to the following categories: ≤2 weeks, >2 weeks and ≤4 weeks, >4 weeks and ≤6 weeks, >6 weeks and ≤8 weeks, and >8 weeks.

### *Titration*

The number and percentage of patients with an up-titration or down-titration in the Renvela group will be described. Patients with a titration are defined as titrated patients according to IVRS/IWRS Week 3a, 4a and 5a, transaction with at least 1 tablet IMP intake afterwards.

**Dose information** will be assessed by the following variables:

- The actual dose received is defined as total IMP dose intake.

- The intended dose is defined as the intended dose according to the initial dose level adjustment and intended dose titration due to phosphorus level or adverse events.

Dose information including average dose, final dose and highest dose will be summarized descriptively (number, mean, SD, median, Q1:Q3, minimum, and maximum).

#### **2.4.3.2 Compliance**

A given administration will be considered noncompliant if the patient did not take the planned dose of treatment as required by the protocol. No imputation will be made for patients with missing or incomplete data.

- 1) Planned dose according to serum phosphorous level per protocol:

Planned dose at visit  $i$  = planned daily dose per serum phosphorus level at visit  $i$  \* duration of the planned dose at visit  $i$

Planned daily dose per phosphorus level at visit  $i$  = planned daily dose adjusted per serum phosphorus level at visit  $i$  based on intended dose before serum phosphorus sampling at visit  $i$

Duration of planned dose at visit  $i$  = date of next phone call visit (visit  $(i+1)a$ ) - date of phone call visit soon after the serum phosphorus sample (visit  $ia$ )

Given no phone call visit for visit  $i$  or visit  $i+1$ , the projected dose start or end date will be the serum phosphorous sampling date +3 days.

- If the first dosing visit of visit 2, planned dose at visit 2 = planned starting daily dose per serum phosphorus level at screening \* (date of visit 2a - first dose date) + planned daily dose per serum phosphorus level at visit 2 \* (date of visit 3a - date of visit 2a)
- For the last scheduled dosing visit, taking visit 5 as an example, planned dose at visit 5 = planned daily dose per serum phosphorus level at visit 5 \* [last dose date - date of last phone call visit (visit 5a)]

- 2) Compliance rate = cumulative actual dose during study / (sum of planned dose per serum phosphorous level for all visits across study) \*100%

Treatment compliance will be summarized descriptively as quantitative variables (number, mean, SD, median, minimum, and maximum). The percentage of patients whose compliance is <80% will be summarized.

Cases of overdose will constitute adverse events and will be listed as such. More generally, dosing irregularities will be listed in [Section 2.2.1](#).

## 2.4.4 Analyses of efficacy endpoints

### 2.4.4.1 Analysis of primary efficacy endpoint

#### 2.4.4.1.1 Primary efficacy analysis

The change from baseline in serum phosphorus at Week 8 as defined in [Section 2.1.3.1](#) will be compared between the Renvela group to the placebo group in the mITT population using stratified Wilcoxon rank sum tests considering randomization strata (screening serum phosphorus [ $\geq 5.5$  -  $6.0$  mg/dL or  $>6.0$  mg/dL]). The statistical test will be two-sided tests at a nominal 5% significance level.

If a patient discontinues the treatment prematurely or does not have serum phosphorus value at Week 8, the last post-baseline on-treatment serum phosphorus measurement during the 8-week double-blind period will be used for the calculation of Week 8 (Last Observation Carried Forward [LOCF] procedure).

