STATISTICAL CONSIDERATIONS	
Sample size determination:
 
To detect a difference of 1 mg/dL in the change from baseline in serum phosphorus between Renvela and placebo at Week 8, 86 patients per arm will provide the power of 90% assuming the common standard deviation is 2 mg/dL (based on data observed in prior study SVCARB03808) with a 2-sided test at the 5% significance level. With expected dropout rate of 15%, the final total sample size will be 202 patients (101 patients in each arm).
 
Analysis Population:
 
• Modified Intention To Treat (mITT) population: The mITT population consists of all patients who are randomized, receive at least one dose of investigational medicinal product (IMP), and have both a baseline assessment and at least one post-baseline assessment of phosphorus measure.• Safety population: The safety population consists of all randomized patients who receive at least one dose of IMP. 
Primary Analysis:
 
The primary efficacy variable (the change from baseline in serum phosphorus at Week 8) will be compared between Renvela and placebo using stratified Wilcoxon rank sum tests considering randomization strata (screening serum phosphorus $\geq 5.5 - 6.0$ mg/dL or > 6.0 mg/dL).
 
Analysis of secondary endpoints
 
Change in total cholesterol, LDL-C, calcium-phosphorus product, iPTH and percentage of patients reaching the target serum phosphorus level (4.6 mg/dL)

	
[1.49 mmol/L], inclusive) at Week 8, and change in serum phosphorus at Week 4 will be analyzed using stratified Wilcoxon rank sum tests using randomization strata (screening serum phosphorus [\geq5.5 – 6.0 mg/dL or $>$6.0 mg/dL]).
 
Percentage of patients reaching the target serum phosphorus level will be compared by treatment assignment (Renvela or placebo) using a Cochran-Mantel-Haensel method stratified by randomization strata (screening serum phosphorus [\geq5.5 – 6.0 mg/dL or $>$6.0 mg/dL]), the odds ratio and 95% confidence intervals will be calculated.

DURATION OF STUDY PERIOD (per patient)	
Study duration is up to 14 weeks.
 
• Screening Period is up to 4 weeks (a 2-week Washout Period is only applicable to eligible patients taking phosphate binder[s] at Screening Visit);• Treatment Period is 8 week;• Post-treatment Period is 2 weeks.

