Objective of this study is to obtain new indication of Renvela in China. Per China regulation, efficacy and safety in a minimum of 200 Chinese patients (100 patients in each arm) is required. This gives a power of 90% for detecting a difference of 1 mg/dL in serum phosphorus. Based on recent meta-analysis of serum level of phosphorus and risk of death and cardiovascular disease in CKD population, all-cause mortality and cardiovascular mortality increased 18% and 10%, respectively, for every 1 mg/dL increase in serum phosphorus (5). This is hence considered clinically relevant.

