11.4.2 Analyses of efficacy endpoints

11.4.2.1 Analysis of primary efficacy endpoint(s)

The change from baseline in serum phosphorus at Week 8 as defined in [Section 9.1](#) will be compared between the Renvela group to the placebo group in the mITT population using stratified Wilcoxon rank sum tests considering randomization strata (screening serum phosphorus [$\geq 5.5 - 6.0$ mg/dL or > 6.0 mg/dL]). The statistical test will be two-sided tests at a nominal 5% significance level.

If a patient discontinues the treatment prematurely or does not have serum phosphorus value at Week 8, the last post-baseline on-treatment serum phosphorus measurement during the 8-week double-blind period will be used for the calculation of Week 8 (Last Observation Carried Forward [LOCF] procedure).

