#### **2.1.4.3 Laboratory safety variables**

The clinical laboratory data consist of hematology (complete blood count [CBC], differential, platelet and prothrombin time), chemistry (serum phosphorus, calcium [adjusted for albumin], albumin, calcium-phosphorus product, chloride, bicarbonate, uric acid, sodium, potassium, glucose, blood urea nitrogen [BUN], alanine aminotransferase [ALT], aspartate aminotransferase [AST], creatinine), and lipid panel (total cholesterol, LDL-C, high-density lipoprotein cholesterol [HDL-C], non-high-density lipoprotein cholesterol [non-HDL-C] and triglycerides). Laboratory variables which are defined as efficacy variables will not be included in the safety analysis.

Clinical laboratory values after conversion will be analyzed into standard international units and international units will be used in all listings and tables.

Blood samples for clinical laboratories will be taken at Visit 1 (Week -4), Visit 2 (Week 0), Visit 3 (Week 2), Visit 4 (Week 4), Visit 5 (Week 6), Visit 6 (Week 8) and/or early termination unless otherwise specified.

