#### 2.4.4.1.2 Sensitivity analysis of primary efficacy endpoint

The following sensitivity analyses will be performed for the primary endpoint.

An analysis of covariance (ANCOVA) with the missing data imputed by LOCF will be performed on the primary efficacy variable. The model will include treatment (Renvela or placebo) and screen serum phosphorus class ( $\geq 5.5$  -  $6.0$  mg/dL [ $1.78$  -  $1.94$  mmol/L] or  $>6.0$  mg/dL [ $1.94$  mmol/L]) and baseline serum phosphorus level as covariates. The adjusted mean difference of primary endpoint between two treatment groups will be provided as well as the 95% confidence interval and P-value.

The Markov Chain Monte Carlo (MCMC) method for multiple imputation will be used to account for missing values in change from baseline in serum phosphorus at Week 8. The imputation model will include baseline serum phosphorus level and all serum phosphorus level at all post-baseline visits stratified by treatment group and screen serum phosphorus class. The seed used for these imputations will be 14011. A minimum value of 0 will be specified in order to avoid negative imputed Phosphorus level.

Missing value in serum phosphorus will be imputed 100 times to generate 100 data sets with complete serum phosphorus values at Week 8. The change from baseline will be derived from observed and imputed serum phosphorus values. The completed data sets will be analyzed using an ANCOVA model with treatment groups, screen serum phosphorus class and baseline serum phosphorus level as covariates. The results from the 100 analyses will be combined using SAS PROC MIANALYZE.

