#### **2.4.4.2 Analyses of secondary efficacy endpoints**

All secondary endpoints will be analyzed using the mITT population.

Descriptive statistics (number, mean, SD, median, Q1, Q3, minimum, and maximum) will be provided by treatment for all continuous secondary variables at the scheduled visits.

All continuous secondary efficacy variables, ie, the change from baseline in serum lipids (total cholesterol and LDL-C), calcium-phosphorus product at Week 8, iPTH at Week 8 and serum phosphorus at Week 4 will be analyzed using the same test described in [Section 2.4.4.1.1](#). For total cholesterol and LDL-C, sensitivity analysis of multiple imputation will not be applied. The same procedure for handling missing assessments/early discontinuation will also be applied as for the primary variable.

Proportion of patients reaching the target serum phosphorus level at Week 8 will be compared by treatment assignment (Renvela or placebo) using a Cochran-Mantel-Haensel method stratified by randomization strata (screening serum phosphorus:  $\geq 5.5 - 6.0 \text{ mg/dL}$  [ $1.78 - 1.94 \text{ mmol/L}$ ] or  $> 6.0 \text{ mg/dL}$  [ $1.94 \text{ mmol/L}$ ]), the proportion difference between Renvela and placebo group and 95% confidence intervals will be calculated.

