## Appendix B Summary of statistical analyses

EFFICACY ANALYSIS		Endpoint	Analysis population	Primary analysis	Supportive analysis	Subgroup analysis	Other analyses
Primary endpoint							
Serum Phosphorus Level Change from baseline at Week 8	miITT	Stratified Wilcoxon rank sum test	ANCOVA Multiple Imputation	Yes			No
Secondary endpoints							
Total cholesterol change from baseline at Week 8	miITT	Stratified Wilcoxon rank sum test	ANCOVA	No			No
LDL-Cat change from baseline at Week 8	miITT	Stratified Wilcoxon rank sum test	ANCOVA	No			No
Calcium-phosphorus product change from baseline at Week 8	miITT	Stratified Wilcoxon rank sum test	ANCOVA Multiple Imputation	No			No
iPTH level change from baseline at Week 8	miITT	Stratified Wilcoxon rank sum test	ANCOVA Multiple Imputation	No			No
Serum Phosphorus level change from baseline at Week 4	miITT	Stratified Wilcoxon rank sum test	ANCOVA Multiple Imputation	No			No
Percentage of patients reaching target serum phosphorus level at Week 8	miITT	Cochran-Mantel-Haensel Method	Yes Multiple Imputation	No			No

SAFETY ANALYSES		Endpoint	Analysis population	Primary analysis	Supportive analysis	Subgroup analysis	Other analyses
Adverse events	Safety			Follow safety guidelines	No	No	No
	Safety			Follow safety guidelines	No	No	No
Deaths	Safety			Follow safety guidelines	No	No	No
Laboratory safety	Safety			Follow safety guidelines	No	No	No
Vital signs	Safety			Follow safety guidelines	No	No	No

Signature Page for VV-CLIN-0540299 v1.0  
efc14011-16-1-9-sap

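### The primary stratified Wilcoxon test is valid, but it does not adjust for continuous baseline phosphorus; a stratified rank ANCOVA would be a modest, optional gain in power if baseline predicts change

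*SAP*

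**What the plan says.** The primary endpoint is the change in serum phosphorus from baseline to Week 8. SAP 2.4.4.1.1 says it "will be compared between the Renvela group to the placebo group in the mITT population using stratified Wilcoxon rank sum tests considering randomization strata", two-sided at 5%, with LOCF for missing Week 8 values. Protocol 11.4.2.1 names the same test ("using stratified Wilcoxon rank sum tests considering randomization strata"), and so does the synopsis ("compared between Renvela and placebo using stratified Wilcoxon rank sum tests considering randomization strata"). The strata are the two screening phosphorus classes, 5.5 to 6.0 mg/dL and above 6.0 mg/dL.

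Baseline is a separate measurement: the last value before the first dose (SAP 2.1.3.1). The mITT definition (SAP 2.3.1.1) requires one for every patient.

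SAP 2.4.4.1.2 then plans an ANCOVA on the same variable, also with LOCF. Its model has treatment, screening class "and baseline serum phosphorus level as covariates. The adjusted mean difference of primary endpoint between two treatment groups will be provided", with a 95% confidence interval and p-value. The ANCOVA is repeated on 100 multiply imputed data sets. Appendix B lists the Wilcoxon test as the primary analysis and the ANCOVA and multiple imputation as supportive.

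On sample size, Protocol section 4 says: "This gives a power of 90% for detecting a difference of 1 mg/dL in serum phosphorus".

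**The concern.** The plan measures phosphorus on a continuous scale just before treatment and treats it as a useful covariate in its sensitivity model. The test that decides the trial, however, adjusts only for a two-level screening class. If baseline predicts change within those classes, part of the variation between patients could be removed at no cost in patients, visits or data. What is at stake is a few points of power. The validity of the test is not in question.

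**Working it through.** **Inputs.** Difference 1 mg/dL, common SD of change 2 mg/dL, two-sided 5%, 90% power by t-test, 15% dropout (SAP 1.3; Protocol 11.1); 86 evaluable per arm (synopsis); 1:1 allocation. The correlation r between baseline and change is not in the documents and is assumed.

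**Step 1: the plan's own figure.** The t-test noncentrality at 86 per arm is 1 / (2 × √(2/86)) = 3.28, which gives power 0.903. At 85 per arm power is just under 0.90, so 86 is reproduced. For dropout, 86 / 0.85 = 101.2, stated as 101.

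**Step 2: power of the planned rank test.** Under normal errors the Wilcoxon test has efficiency 3/π = 0.955 relative to the t-test.
- 86 × 0.955 = 82.1 effective per arm: power 0.890.
- 101 × 0.955 = 96.4 effective per arm: power 0.933.

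LOCF keeps any mITT patient with a post-baseline value, so the analysed number should lie between 86 and 101.

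**Step 3: planned test against stratified rank ANCOVA, by simulation.** The SD of change is 2, the true difference 1, and errors are normal. Two assumed phosphorus distributions were used:
- A: 35% of patients in the lower class, screening-baseline correlation 0.7, 10,000 trials per cell.
- B: screening value 5.5 plus a gamma variable (shape 1.2, scale 0.9), baseline equal to screening plus noise of SD 0.5, 4,000 trials per cell; r = 0.4 was not included.

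Power in %, stratified Wilcoxon → rank ANCOVA, with the gain in points:

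| r | A, 86 per arm | B, 86 per arm | A, 101 per arm | B, 101 per arm |
|---|---|---|---|---|
| 0 | 88.8 → 88.5 (-0.3) | 88.9 → 87.8 (-1.1) | 93.1 → 92.9 (-0.2) | 93.3 → 93.1 (-0.3) |
| 0.3 | 89.6 → 90.7 (+1.1) | 89.4 → 90.5 (+1.2) | 93.9 → 94.8 (+0.9) | 93.3 → 94.1 (+0.8) |
| 0.4 | 90.6 → 93.1 (+2.5) | – | 93.7 → 95.6 (+1.9) | – |
| 0.5 | 90.8 → 94.9 (+4.1) | 92.1 → 95.1 (+3.1) | 94.4 → 97.3 (+2.9) | 95.0 → 97.1 (+2.1) |

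Gains are taken from unrounded powers where available. At power near 0.9 the standard error of one cell is √(0.9 × 0.1 / 10,000) = 0.3 points for A and √(0.9 × 0.1 / 4,000) = 0.5 points for B.

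Further runs varied A at 86 per arm, with the lower class at 20% or 50% and the screening-baseline correlation at 0.5 or 0.9. The gain was -0.5 to -0.3 at r = 0, +0.3 to +1.6 at 0.3, +1.4 to +3.3 at 0.4 and +2.6 to +5.1 at 0.5. Type I error was about 4.5% to 5.5% for both tests throughout.

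**Step 4: is r likely to differ from zero?** Baseline is part of the change score. If baseline and Week 8 have equal SDs and correlation c, then r = -(1 - c) / √(2(1 - c)) = -√((1 - c)/2).
- c = 0.4: |r| = √0.3 = 0.55.
- c = 0.8: |r| = √0.1 = 0.32.

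The equal-SD assumption matters. In general the covariance of baseline with change is SD(baseline) × [c × SD(Week 8) - SD(baseline)]. It vanishes if SD(baseline) = c × SD(Week 8). The entry threshold of 5.5 mg/dL could narrow the baseline spread and so bring |r| down.

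**Step 5: two limiting cases.**
- If the true difference were that of the cited dialysis study, 2.14 - 0.19 = 1.95 mg/dL (a different population), both tests have at least 99.9% power at 86 per arm.
- With heavy-tailed errors (t, 3 df), power runs from 99.2 → 99.2 at r = 0 to 98.2 → 99.6 at r = 0.5, a gain of 0 to 1.4 points.

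**The case against.** The strongest reply is that this is a preference between two valid tests. Baseline already enters the primary analysis, because it is subtracted in the change score and the screening strata partly capture it. A baseline-adjusted analysis already follows as a sensitivity analysis. The gain rests on a correlation that the documents do not give. LOCF moves the analysed number towards 101 per arm, where the gain is below 1 point at r = 0.3, and heavy tails shrink it further. Randomization began on 21 July 2016 (SAP 1.5), and amending a primary test in a running trial is not trivial.

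All of this stands as a limit on size and priority. It does not change the fact that the deciding test omits a covariate that every analysed patient has and that the sponsor's own model uses.

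A reader might also infer that the primary endpoint has no effect estimate, since SAP 2.4.4.1.1 names only a test. The documents do not support that: SAP 2.4.4.1.2 plans the LOCF ANCOVA difference with its 95% interval for the same variable. Nor is it open which p-value decides. Appendix B separates primary from supportive analyses, and SAP 2.4.4.3 ties the fixed sequence to the primary parameter at 0.05.

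**Conclusion.** The point holds as an optional improvement. The planned test keeps its type I error and has about 89% to 93% power under the plan's assumptions. Replacing it with a stratified rank ANCOVA would change power at 86 per arm by about 0 to -1 point at r = 0, +1 at 0.3, +2.5 at 0.4 and +3 to +4 at 0.5. At 101 per arm the gain is about 1 to 3 points for r of 0.3 to 0.5. These figures assume normal errors, SD 2, a true difference of 1 mg/dL and the phosphorus distributions described above. A correlation of 0.3 to 0.55 is plausible if baseline and Week 8 SDs are similar and their correlation is 0.4 to 0.8, but that too is assumed. Nothing is gained if the true difference is near 1.95 mg/dL.

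Three stronger readings should be avoided: that the primary test is invalid or underpowered, that baseline is wholly unused, and that significance corresponds to a fixed observed difference of about 0.60 mg/dL. The last figure is a t-test half-width, 1.974 × 2 × √(2/86) = 0.60. A rank test has no such threshold in mean difference.

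**What to change.** Before unblinding:

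1. Make the primary test a stratified rank ANCOVA on change. Within each screening class, rank the change and the baseline phosphorus, regress the first ranks on the second with both arms pooled, and apply the same stratified test to the residuals. Keep LOCF and the mITT population.
2. Keep the unadjusted stratified Wilcoxon test as a sensitivity analysis.
3. State whether the five continuous secondary endpoints in the fixed sequence follow, each with its own baseline, or keep the unadjusted test.

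No patient, visit or measurement is added, and the sample size stays the same. The cost is a protocol amendment (synopsis and 11.4.2.1, and 11.4.2.2 if the secondary endpoints follow) with IRB/IEC approval under Protocol section 15, plus edits to SAP 2.4.4.1.1, 2.4.4.1.2, 2.4.4.2 and Appendix B. There is also a possible loss of up to about 1 point of power if r is near zero. The sponsor may reasonably decide that the gain does not justify an amendment.

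Separately, and as reporting only, one SAP sentence could say that the planned LOCF ANCOVA difference with its 95% interval is shown beside the primary p-value. Rank ANCOVA gives no estimate in mg/dL, so that sentence would serve whichever test is kept.
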